3.2 Exclusion Criteria

- 3.2.1 Patients who have had chemotherapy or radiotherapy within 2 weeks (6 weeks for nitrosoureas or mitomycin C) prior to entering the study or those who have not recovered from adverse events due to agents administered more than 2 weeks earlier.
- 3.2.2 Patients may not be receiving any other investigational cancer-directed agents.
- 3.2.3 History of allergic reactions attributed to compounds of similar chemical or biologic composition to MGE.
- 3.2.4 Patients unable to take oral medications or those with history of malabsorption due to bowel resection or gastrointestinal disease.
- 3.3.5 Patients with uncontrolled diarrhea or persistent nausea/vomiting requiring daily antiemetic therapy for symptom management within the past 21 days
- 3.2.6 Uncontrolled intercurrent illness including, but not limited to ongoing or active infection, symptomatic congestive heart failure, unstable angina

pectoris, cardiac arrhythmia, or psychiatric illness/social situations that would limit compliance with study requirements.

- 3.2.7 Pregnant women are excluded from this study because of potential for teratogenic or abortifacient effects with using MGE. Because there is an unknown but potential risk for adverse events in nursing infants secondary to treatment of the mother with MGE, breastfeeding should be discontinued.
- 3.2.8 Patients with primary brain tumors are excluded due to lack of data on MGE crossing the blood brain barrier. Patients with metastatic brain tumors may be enrolled.

3.3 Inclusion of Women and Minorities

Men and women of all races and ethnicities who meet the above-described eligibility criteria are eligible to participate in this study.

The study consent form will also be provided in Spanish for Spanish-speaking participants. We anticipate enrolling between 2 and 30 participants on this study. Based on CCCWFU population estimates, we expect approximately 40% of participants to be women. Translating this to our maximum sample size estimate of 30, we plan to enroll at least 12 women if we reach our maximum accrual. We do not expect the percentage of Hispanic/Latino or racial minority cancer patients eligible for this study to be higher than the percentage of Hispanic or racial minority new cancer patients seen at CCCWFU (1.7% and 14.4%, respectively); therefore, we plan to enroll at least 4 racial minority and 1 Hispanic/Latino patient if we reach our maximum accrual.

Should we not meet or exceed these estimates, the PI will engage the Cancer Center Health Equity Advisory Group to discuss strategies to enhance recruitment in these target populations.

4.0 Registration Procedures

Patients **must** be registered prior to the initiation of treatment.

You must perform the following steps in order to ensure prompt registration of your patient:

- 1. Complete the Eligibility Checklist (Appendix B)
- 2. Complete the Protocol Registration Form (Appendix A)
- 3. Alert the Cancer Center registrar by phone, *then* send the signed Informed Consent Form, Eligibility Checklist and Protocol Registration Form to the registrar, either by fax or e-mail. Protocol Registration is open from 8:30 AM 4:00 PM, Monday-Friday.

Contact Information: Protocol Registrar [contact] Protocol Registrar [contact] Protocol Registrar E-MAIL ([contact])

4. Fax/e-mail ALL eligibility source documents with registration. Patients **will not** be registered without all required supporting documents.

Note: If labs were performed at an outside institution, provide a printout of the results. Ensure that the most recent lab values are sent.

To complete the registration process, the Registrar will:

- assign a patient study number
- assign the patient a dose
- register the patient on the study

5.0 Study Outcomes and Study Measures

5.1 Primary Outcome

5.1.1 The primary outcome measure will be dose limiting toxicity (DLT) assessed by SAEs in patients with metastatic cancer receiving MGE under the proposed regimen at 4 weeks.

5.2 Secondary Outcomes

- 5.2.1 Adverse events/toxicity at weeks 4, 8 and every 4 weeks thereafter if remain on treatment
- 5.2.2 Identification of measured phenolic levels (total and component phenolics) at baseline,4, and 8 weeks
- 5.2.3 Evaluate change in systemic cytokines, growth factors from baseline to 4 and 8 weeks including but not limited to: TNF α , IL6, IL6R, IL8, IL1 α , IL1 β , IGF-1, VEGF
- 5.2.4 Overall response rate (CR, PR, and SD) at 8 weeks.
- 5.2.5 PFS and OS in patients with metastatic cancer receiving MGE under the proposed regimen.
- 5.2.6 Quality of life in cancer patients taking MGE using the Functional Assessment of Cancer Therapy–General (FACT-G) measure and fatigue, as measured by the PROMIS Fatigue-Short Form.
- 5.2.7 Adherence to MGE treatment, as assessed by patient-reported medication logs and pill count every 4 weeks while on treatment.

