2.2 Secondary Objectives

- 2.2.1 To monitor adverse events/toxicity every 4 weeks while on treatment
- 2.2.2 To evaluate change in phenolic levels (total and component, blood and urine) from baseline to 4 and 8 weeks on MGE
- 2.2.3 To evaluate change in serum cytokines and growth factors from baseline to 4 and 8 weeks on MGE
- 2.2.4 To observe the response rate of MGE in patients with metastatic cancer.
- 2.2.5 To assess overall and progression-free survival in patients with metastatic cancer receiving MGE.
- 2.2.6 To assess global quality of life (FACT-G) and fatigue (PROMIS-fatigue short form) in cancer patients taking MGE.
- 2.2.7 To assess adherence to MGE treatment.

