6.0 Treatment Plan

6.1 Study-Related Activities

Measures / Forms	Pre- Study ^a	Baseline	Week 2 ^h	Week 4 ^j	Week 8 ^k	Every 4 weeks ^k	Off-study
Informed consent	Х						
Demographics	Х						
Medical history	Х			Х	Х	Х	
Concurrent meds	Х			Х	Х	Х	
Physical exam	Х			Х	Х	Х	
Vital signs	Х			Х	Х	Х	
Weight		Х					
Height		Х					
ECOG Performance Status	Х			Х	Х	Х	
Pill Diary		Х		Х	Х	Xi	
Adherence assessment			Х	Х	Х		
Quality of life and fatigue assessments		х		х	Х	Х	
Tumor measurement by imaging ^b	Х				Х	Xp	
Tumor markers (if applicable) ^c		Х		Х	Х		
CBC w/diff, platelets	Х	Х		Х	Х	Х	
Serum chemistries ^d	Х	Х		Х	Х	Х	
B-HCG ^e	Х						
INR check ^f			Х				
Phenolic levels (blood and urine)		Х		Х	Х		
Research labs (cytokines and growth factors)		Х		х	х		
Adverse event evaluation		Х	Х	Х	Х	Х	
Vital status ^g							Х

^a Pre-study imaging listed in table must be completed **within** 42 days prior to registration. Additional pre-study activities need not be repeated if performed within 10 days of starting study drug.

^b CT imaging or other imaging modality will be obtained at baseline (within 42 days of registration) and at 8 weeks (± 7 days). Imaging will then be q12 weeks (± 28 days) for as long as the patient remains on study. CT, PET/CT, or MRI are acceptable imaging modalities and all imaging will be considered per standard of care for patients on active cancer treatments.

^c Tumor-specific markers may include but are not limited to testosterone level and PSA for prostate cancer patients, CEA for colorectal patients, and CA19-9 for pancreatic cancer patients as performed per standard of care.

^d Albumin, alkaline phosphatase, total bilirubin, bicarbonate, BUN, calcium, chloride, creatinine, glucose, potassium, total protein, SGOT[AST], SGPT[ALT], sodium.

^e Serum pregnancy test (women of childbearing potential).

^f Patients taking warfarin will have INR checked within 2 weeks of starting MGE. This can be performed locally.

^g Vital status will be assessed by chart review or phone every 6 weeks (± 14 days) after patient comes off study.

^h Phone contact will occur 2 weeks after each clinic visit (± 3 days) until the Week 8 visit is complete. ⁱ Patients will not be asked to complete a pill diary after 6 cycles (24 weeks).

^jWeek 4 study appointments will be scheduled at day 28 ±3 days.

^k Study appointments at Week 8 and after will be scheduled 28 days after the prior appointment, ± 7 days

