6.6 Duration of Follow Up

Patients removed from the study for unacceptable adverse events will be followed until resolution or stabilization of the adverse event. Patients who are removed or withdraw from the study for any reason other than toxicity will be followed for vital status only after the 24 hour washout period. Patients will be followed every 6 ± 2 weeks until death for monitoring survival study endpoints.

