7.2 Methods for Evaluation of Measurable Disease

The same method of assessment and the same technique should be used to characterize each identified and reported lesion at baseline and during follow-up whenever possible. Measurements will be obtained from usual care imaging and assessed by the PI(s) in confirmation with the physician of record.

- CT is the best currently available and reproducible method to measure lesions selected for response assessment. MRI and PET/CT are also acceptable.
- Lesions on a chest X-ray may be considered measurable lesions if they are clearly defined and surrounded by aerated lung. However, CT is preferable.
- Clinical lesions will only be considered measurable when they are superficial and ≥10 mm in diameter as assessed using calipers. For the case of skin lesions, documentation by color photography, including a ruler to estimate the size of the lesion, is recommended.
- Tumor markers alone will not typically be used to define response. If markers are initially above the upper normal limit, they must normalize for a patient to be considered in complete response.
- Cytology and histology can be used in rare cases (e.g., for evaluation of residual masses to differentiate between Partial Response and Complete Response or evaluation of new or enlarging effusions to differentiate between Progressive Disease and Response/Stable Disease).

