12.2 Analysis of Secondary Objective

12.2.1 To monitor toxicity at 4, 8, and every 4 weeks thereafter on MGE

To analyze objective 2.1.1, we will summarize any expected toxicities, any laboratory based toxicities, and any grade 3 or higher gastrointestinal toxicities and any grade 4 or higher toxicities using frequency tables overall and by week.

12.2.2 To evaluate change in phenolic levels (total and component, blood and urine) from baseline to 4 and 8 weeks

To analyze objective 2.2.2, we will fit a mixed model ANOVA model with phenolic level as the outcome and time (baseline, 4, and 8 weeks) as a fixed effect and subject as a random effect. We will use contrasts to estimate the changes from baseline to week 4 and week 8.

12.2.3 To evaluate change in serum cytokines and growth factors from baseline to 4 and 8 weeks on MGE

To analyze objective 2.2.3, we will fit a mixed model ANOVA model with the outcome of interest (cytokine or growth factor) as the outcome and time (baseline, 4, and 8 weeks) as a fixed effect and subject as a random effect.

We will use contrasts to estimate the changes from baseline to week 4 and week 8.

12.2.4 To observe the response rate of MGE in patients with metastatic cancer.

To analyze objective 2.2.4, we will characterize response at 8 weeks using frequency table. We will also characterize the best response at the end of treatment with MGE using a frequency table.

12.2.5 To assess overall and progression-free survival in patients with metastatic cancer receiving MGE.

To analyze objective 2.2.5, we will summarize overall survival and progression-free survival using the Kaplan-Meier method. We will calculate median survival rates and associated 95% confidence intervals. Patients will be censored at date of last contact.

12.2.6 To assess global quality of life and fatigue in cancer patients taking MGE.

Quality of Life and fatigue will be monitored every 4 weeks until the end of the study. To analyze objective 2.2.6, we will fit a mixed model ANOVA model with phenolic level as the outcome and time (baseline, every 4 weeks) as a fixed effect and subject as a random effect. We will use contrasts to estimate the changes from baseline to each follow-up time period.

12.2.7 To assess adherence to MGE treatment.

To analyze objective 2.2.7, we will summarize the percent of pills taken at the end of every 4 week period i using the formula:

Percent of pills taken_i =

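### Stable disease counts towards the response rate, and PFS runs to progression although no tumour assessment is scheduled after a patient leaves the study

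*Combined protocol and SAP*

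**What the plan says.** **Response.** The objective in Section 2.2.4 is "To observe the response rate of MGE in patients with metastatic cancer". The outcome serving it, in Section 5.2.4, is "Overall response rate (CR, PR, and SD) at 8 weeks". Section 7.2, on cytology and histology, says they may be used "to differentiate between Progressive Disease and Response/Stable Disease", so there stable disease is named apart from response. Section 12.2.4 plans frequency tables of week-8 response and of best response, and does not say which categories make up the rate.

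**PFS.** Section 7.1 runs PFS from start of treatment to progression or death, and says that follow-up continues to progression and death. Note b of the schedule in Section 6.1 provides imaging "for as long as the patient remains on study", and Section 7.0 ties it to time on MGE. After that, note g says "Vital status will be assessed by chart review or phone every 6 weeks", and vital status is the only item in the off-study column. Under Section 6.6, patients who leave for reasons other than toxicity "will be followed for vital status only after the 24 hour washout period". The last sentence of 6.6 continues contact "until death for monitoring survival study endpoints" but names no progression assessment. For OS and PFS together, Section 12.2.5 has one rule: "Patients will be censored at date of last contact".

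**The concern.** CR, PR and SD added together are disease control. In a single-arm study of patients with metastatic or unresectable tumours, some will be stable at 8 weeks whatever the agent does. Calling the sum a response rate allows a figure well above zero to be reported with no tumour having shrunk. The label has one use inside the trial: Section 12.1 lets observed anti-tumour efficacy inform the decision on further escalation after level 5.

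For PFS, the endpoint needs a progression date that the schedule stops collecting once the patient is off study. Sections 6.2.2, 6.5 and 6.5.1.2 all foresee patients leaving for reasons other than progression. If such a patient progresses later and nobody records it, the PFS time runs on to death, or to the last contact at which the patient was known to be alive. Either way PFS is lengthened.

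**Working it through.** **Plan's own figure.** Section 12.3 gives a maximum of 30 patients. Five dose levels × 6 patients per level = 30, which reproduces it. No target or power is stated for response or PFS, so what follows is illustration on stated assumptions.

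**Response.**
- Rate under 5.2.4 minus the CR+PR rate = (CR+PR+SD)/N − (CR+PR)/N = SD/N.
- 9 SD and no CR/PR of 30: 9/30 = 30% (exact 95% CI 14.7 to 49.4%), against 0/30 = 0% (0 to 11.6%).
- 5 SD and no CR/PR of 15: 5/15 = 33% (11.8 to 61.6%), against 0/15 = 0% (0 to 21.8%).
- Inert agent, exponential time to progression with assumed median m months, 56 days = 1.84 months: share progression-free at week 8 = 0.5^(1.84/m). For m = 1, 2, 3, 4 this is 28, 53, 65, 73%. These are upper bounds on the 5.2.4 rate, because a patient without week-8 imaging is not evaluable (Section 7.1) and Section 7.0 restricts assessment to measurable disease.

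**PFS: the passages side by side.**

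| Question | Place | Answer |
|---|---|---|
| When does PFS end? | 7.1 | Progression or death |
| How long is follow-up? | 7.1 | To progression and death |
| When is imaging done? | 6.1 note b; 7.0 | On study; on MGE |
| What is collected off study? | 6.1 note g; 6.6 | Vital status (plus adverse-event follow-up after toxicity) |
| Where is PFS censored? | 12.2.5 | Last contact, as for OS |

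The second row cannot be met from the third and fourth. If the last three are followed as written, later progression is missed.

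**PFS: size.** Simulation with exponential times, true median 2.0 months, on-study progression dates taken as exactly known. A patient who leaves before progression has an event only at death; everyone else has it at progression. Each cell is the median PFS in months.

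*Leaving unrelated to progression* (mean exit time 1.5 months, median survival after progression 4 months):

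| Leaving | 0% | 7% | 13% | 26% | 39% |
|---|---|---|---|---|---|
| Plan | 2.00 | 2.11 | 2.25 | 2.58 | 3.08 |
| Status recorded 6-weekly | 2.00 | 2.05 | 2.10 | 2.20 | 2.30 |

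*Leaving shortly before progression* (mean 0.3 month before):

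| Leaving | 5% | 10% | 20% | 30% | 40% |
|---|---|---|---|---|---|
| Plan, survival after progression 1 month | 2.08 | 2.14 | 2.30 | 2.45 | 2.62 |
| Status 6-weekly, 1 month | 2.05 | 2.08 | 2.18 | 2.26 | 2.34 |
| Plan, survival after progression 4 months | 2.13 | 2.28 | 2.59 | 2.98 | 3.44 |
| Status 6-weekly, 4 months | 2.07 | 2.13 | 2.23 | 2.34 | 2.44 |

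At 13% leaving, the 4-month plan row gives about 2.36. Shifts are therefore about 0.1 to 0.4 month at 5 to 13% leaving (2.08 − 2.00 to 2.36 − 2.00), and about 0.6 to 1.5 months at about 40% (2.62 − 2.00 to 3.44 − 2.00).

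**Source of the bias.** With an assumed data cut-off between 1 and 16 months and leaving unrelated to progression, 52% of leavers are censored at last contact, and the plan still gives 2.24 at 13% leaving. The shift comes from progression that is not recorded, whether the time then ends in death or in censoring.

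**Sampling error.** With a true median of 2.0 and no censoring, 95% of observed medians lie between about 0.9 and 3.8 months at N = 15, and between 1.1 and 3.1 at N = 30.

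**The case against.** **On response,** the components stand beside the label, and frequency tables would normally give CR, PR and SD their own rows. A reader might infer that stable disease will be passed off as shrinkage; the documents do not support that. What stands against the plan is narrower: the tables do not redefine the rate, and the named outcome still includes SD. The denominators of 15 and 30 are illustrative, since the evaluable number is not known.

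**On PFS,** a reader might infer that progression is never captured off study. The documents do not go so far. Section 7.1 and the end of 6.6 state a wider intent. Off-study contact may be by chart review of patients recruited at one cancer centre, where usual-care scans may be on file. The form list under Section 11.0 includes a treatment response evaluation, an end-of-treatment best-response evaluation, an off-study form and a survival form (Appendices D, E, M and N), none of which is shown. These could close the gap. The exit forms would not by themselves record progression that comes later, and no passage shown tells staff to seek it.

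**On size,** four of the five stopping criteria in Section 6.5 are not headed progression, but that counts list items, not patients. Some of those exits may themselves be clinical progression, which is already a PFS event. The size also depends on how progression is dated. With leaving unrelated to progression at 7 to 13%, dating at 4-weekly visits gives a median of 2.76 months with or without leaving. Dating by the imaging schedule alone gives about 3.4 without leaving and 3.7 to 4.0 with it. This objection stands: the direction is clear, but the size is not fixed by the documents.

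**Conclusion.** Both parts hold as faults of definition and follow-up.

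The response rate in 5.2.4 exceeds CR+PR by exactly SD/N and can be well above zero without shrinkage. The frequency tables limit the harm but do not remove it.

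The follow-up passages for PFS are unreconciled. Followed as written, they can overstate PFS, unless the forms not shown capture progression. The size is conditional on an assumed 2-month median, exactly known on-study progression dates and an unknown leaving rate: zero if nobody leaves this way, about 0.1 to 0.4 month at 5 to 13%, about 0.6 to 1.5 months at about 40%. At low leaving rates this is small against sampling error with 30 patients or fewer.

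It would be tempting to conclude that reported PFS will be wrong by a known amount, or that the dose finding is compromised. Neither follows. No leaving rate is documented, both endpoints are secondary and descriptive, and the MTD rests on DLTs alone. The one link to escalation is the mention of anti-tumour efficacy in Section 12.1, which applies only if no MTD is found by level 5.

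**What to change.** 1. **Response.** In 5.2.4 and 12.2.4, define response as CR+PR. Report CR+PR+SD separately as disease control, each with its evaluable denominator.
2. **Follow-up.** Reconcile Sections 6.1, 6.6 and 7.1 by recording progression status and date at the 6-weekly chart review or call already scheduled, if the forms do not already do so. In the scenarios above this removes roughly 40 to 80% of the shift. For example, at 39% unrelated leaving it falls from 1.08 to 0.30 month.
3. **Censoring.** Keep last-contact censoring for OS only. Censor PFS without progression or death at the last disease assessment, including status obtained at the off-study contacts. The new rule should not stand in for item 2. If patients leave shortly before progression, censoring at the last on-study assessment alone gives 3.02 at 40% leaving with 1-month survival after progression, against 2.62 under the plan.
4. **Optional.** A sensitivity analysis may count leaving without progression as an event, labelled as a lower bound. It is itself biased: 1.60 against a true 2.00 at 13% unrelated leaving.

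The cost is wording in the protocol and its statistical section, and at most one item added to an existing contact. The response figure will look less favourable and PFS will carry more censoring. Progression dates not collected during follow-up may not be recoverable afterwards.

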6.0 Treatment Plan

6.1 Study-Related Activities

Measures / Forms	Pre- Study ^a	Baseline	Week 2 ^h	Week 4 ^j	Week 8 ^k	Every 4 weeks ^k	Off-study
Informed consent	Х						
Demographics	Х						
Medical history	Х			Х	Х	Х	
Concurrent meds	Х			Х	Х	Х	
Physical exam	Х			Х	Х	Х	
Vital signs	Х			Х	Х	Х	
Weight		Х					
Height		Х					
ECOG Performance Status	Х			Х	Х	Х	
Pill Diary		Х		Х	Х	Xi	
Adherence assessment			Х	Х	Х		
Quality of life and fatigue assessments		х		х	Х	Х	
Tumor measurement by imaging ^b	Х				Х	Xp	
Tumor markers (if applicable) ^c		Х		Х	Х		
CBC w/diff, platelets	Х	Х		Х	Х	Х	
Serum chemistries ^d	Х	Х		Х	Х	Х	
B-HCG ^e	Х						
INR check ^f			Х				
Phenolic levels (blood and urine)		Х		Х	Х		
Research labs (cytokines and growth factors)		Х		х	х		
Adverse event evaluation		Х	Х	Х	Х	Х	
Vital status ^g							Х

^a Pre-study imaging listed in table must be completed **within** 42 days prior to registration. Additional pre-study activities need not be repeated if performed within 10 days of starting study drug.

^b CT imaging or other imaging modality will be obtained at baseline (within 42 days of registration) and at 8 weeks (± 7 days). Imaging will then be q12 weeks (± 28 days) for as long as the patient remains on study. CT, PET/CT, or MRI are acceptable imaging modalities and all imaging will be considered per standard of care for patients on active cancer treatments.

^c Tumor-specific markers may include but are not limited to testosterone level and PSA for prostate cancer patients, CEA for colorectal patients, and CA19-9 for pancreatic cancer patients as performed per standard of care.

^d Albumin, alkaline phosphatase, total bilirubin, bicarbonate, BUN, calcium, chloride, creatinine, glucose, potassium, total protein, SGOT[AST], SGPT[ALT], sodium.

^e Serum pregnancy test (women of childbearing potential).

^f Patients taking warfarin will have INR checked within 2 weeks of starting MGE. This can be performed locally.

^g Vital status will be assessed by chart review or phone every 6 weeks (± 14 days) after patient comes off study.

^h Phone contact will occur 2 weeks after each clinic visit (± 3 days) until the Week 8 visit is complete. ⁱ Patients will not be asked to complete a pill diary after 6 cycles (24 weeks).

^jWeek 4 study appointments will be scheduled at day 28 ±3 days.

^k Study appointments at Week 8 and after will be scheduled 28 days after the prior appointment, ± 7 days

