7.0 Measurement of Effect

Although response is not the primary endpoint of this trial, patients with measurable disease will be assessed by the treating physician, based on the clinical radiologic report and clinical status, per usual care. For the purposes of this study, patients will be reevaluated with imaging 8 weeks (± 7 days) after study initiation and then every 12 weeks (± 28 days) while on MGE.

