7.1 Definitions

Evaluable for toxicity (primary outcome): All patients will be evaluable for toxicity from the time of their first treatment with MGE. Per section 6.5.1, patients who miss 7 consecutive days of treatment in the first 28 days for reasons other than toxicity are not evaluable and will be removed from the study and replaced.

Inevaluable for objective response: When no imaging/measurement is done at all at a particular time point, the patient is not evaluable (NE) at that time point.

Measurable disease: Measurable lesions are defined as those that can be accurately measured in at least one dimension (longest diameter in the plane of measurement is to be recorded) with a minimum size of 10 mm by CT scan, 10 mm caliper measurement by clinical exam, or 20 mm by chest X-ray.

Non-measurable lesions: Non-measurable lesions include: bony metastases, leptomeningeal disease, ascites, pleural or pericardial effusion, inflammatory breast disease, lymphangitic involvement of skin or lung, abdominal masses or organomegaly identified by physical exam that is not measurable by reproducible imaging techniques.

Progression-Free Survival is defined as the duration of time from the start of treatment to the time of progression or death. Patients will be followed until disease progression and death.

Overall Survival is defined as the duration of time from the start of treatment to date of death.

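### Baseline imaging is not required to follow the last prior anticancer treatment, so in some eligible patients up to 28 days of chemotherapy or radiotherapy can be counted in the uncontrolled response tables for MGE

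*Combined protocol and SAP*

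**What the plan says.** - **Baseline scan.** Section 6.1, footnote a: "Pre-study imaging listed in table must be completed within 42 days prior to registration". Footnote b repeats the limit and adds the first follow-up scan: imaging "will be obtained at baseline (within 42 days of registration) and at 8 weeks (± 7 days"). The 10-day limit in footnote a applies to the other pre-study activities, not to imaging.
- **Prior treatment.** Section 3.2.1 excludes "Patients who have had chemotherapy or radiotherapy within 2 weeks (6 weeks for nitrosoureas or mitomycin C) prior to entering the study". It gives no interval for other kinds of prior anticancer treatment.
- **Start of dosing.** Section 4.0: "Patients must be registered prior to the initiation of treatment". No maximum gap between registration and first dose is given.
- **Use of the scan.** Section 7.2 asks for the same method and technique "to characterize each identified and reported lesion at baseline and during follow-up whenever possible", so the baseline scan is the reference. Section 7.0 says "patients will be reevaluated with imaging 8 weeks (± 7 days) after study initiation".
- **Outcomes.** Section 5.2.4 is "Overall response rate (CR, PR, and SD) at 8 weeks". Section 12.2.4 reports response at 8 weeks and best response as frequency tables. PFS in section 7.1 "is defined as the duration of time from the start of treatment to the time of progression or death" and is summarised by Kaplan-Meier (section 12.2.5).

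None of these sections requires the baseline scan to come after the last prior treatment, or to be repeated if treatment followed it.

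**The concern.** The imaging window and the exclusion window were set separately and do not fit together. A patient could be scanned six weeks before registration, receive chemotherapy or have a measured lesion irradiated over the next four weeks, stop two weeks before entry and be fully eligible. The week 8 scan would then be compared with one taken before that treatment. Because stable disease counts towards the response rate, earlier treatment need only have held growth back to affect the result.

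In a patient with no treatment after the scan, an old scan acts in the other direction. Growth before the first dose is included in the week 8 comparison and can be read as lack of response, or as early progression.

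Objective 2.2.4 describes the result as the response rate of MGE. There is no control arm, and no adjustment for scan age or recent therapy is planned. The readout also has a possible use inside the trial: if no MTD is found after level 5, section 12.1 lists anti-tumour activity among the considerations for the decision on further escalation.

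**Working it through.** **The plan's own figure.** Section 12.3 gives a maximum of 30 patients. Section 12.1 has 5 dose levels with at most 6 patients each: 5 × 6 = 30, which reproduces it. The point does not depend on this figure except for the weight of one patient in step 4.

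**Inputs.** Maximum scan age at registration: 42 days (6.1). Exclusion interval: 14 days, or 42 days for nitrosoureas or mitomycin C (3.2.1). Week 8 scan: day 49, 56 or 63 (6.1, 7.0). Assumptions: study entry and registration are the same date; week 8 is counted from first dose; the gap g from registration to first dose is 0 days, with 14 days shown as an alternative.

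**1. Treatment that can follow the reference scan.** Overlap = scan window - exclusion interval.
- Most chemotherapy, and radiotherapy: 42 - 14 = 28 days.
- Nitrosoureas or mitomycin C: 42 - 42 = 0 days.

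**2. Share of the scan-to-scan interval before MGE.** Share = (42 + g) / (42 + g + t), where t is the day of the week 8 scan.

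| t (days) | g = 0 | g = 14 |
|---|---|---|
| 49 | 42/91 = 46% | 56/105 = 53% |
| 56 | 42/98 = 43% | 56/112 = 50% |
| 63 | 42/105 = 40% | 56/119 = 47% |

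These are the largest shares at each g. A patient with a recent scan has a much smaller one.

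**3. What that share can do to a size change.** Assume constant exponential growth with no effect of MGE. The documents give neither a growth rate nor a size threshold for progression, so a range is shown. For a total increase T over 98 days, the part before MGE is (1 + T)^(42/98) - 1 and the part on MGE is (1 + T)^(56/98) - 1.
- T = 10%: about 4% before and 6% on MGE.
- T = 20%: about 8% before and 11% on MGE.
- T = 30%: about 12% before and 16% on MGE.

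If a 20% threshold is assumed, scan age alone changes the category only for tumours that take between 56 and 98 days to grow by 20%. At 70 days, for example, 1.2^(56/70) = 1.157 stays below the threshold, while 1.2^(98/70) = 1.291 exceeds it. Faster or slower tumours are classified the same way with either scan age.

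**4. Weight of one patient.** One misclassified patient moves the response rate by 1/30 = 3.3 percentage points if all 30 are evaluable, or by 1/15 = 6.7 points if 15 are (assumption).

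**The case against.** The strongest reply is that little depends on this. The primary outcome is DLT at 4 weeks. Section 7.0 says that response is not primary, and section 12.2.4 plans a table with no test or threshold. With 2 to 30 patients of mixed tumour types over five dose levels, response could support no formal efficacy claim even with ideal baselines. Imaging is usual care, so a 42-day window is an understandable practical choice. The overlap also needs a particular sequence: an old scan, then further treatment, then entry with no newer scan. Section 3.1.1 mainly admits patients who have failed standard therapy, in whom carried-over shrinkage may be uncommon. Assessment also draws on the radiology report and clinical status. Finally, the eligibility checklist and the baseline and response forms are separate attachments that cannot be seen here; they may already record the relevant dates or hold response rules.

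Most of this stands, and it limits the importance of the point. It does not close the gap: section 3.1.1 does not rule the sequence out, and nothing in the protocol text prevents it.

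A reader might infer more than the documents support:
- **That the reported response rate of MGE will be inflated.** The plan permits carry-over in some patients and does not make it general. Growth before MGE works against it, and no document gives the usual scan age.
- **That two weeks is the only washout.** Section 3.2.1 sets six weeks for two drug groups, and there the overlap vanishes.
- **That timing PFS from the start of treatment is a mistake.** It is a legitimate origin. The weakness is only that the reference scan may be much older than that origin.

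**Conclusion.** The point holds as a gap in the rules for secondary, descriptive outcomes. Taking entry and registration as the same date, up to 28 days of chemotherapy or radiotherapy other than nitrosoureas or mitomycin C can follow the scan used as the response baseline. Its effect can then appear as CR, PR or SD in the 8-week and best-response tables.

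Separately, up to 42 of 98 days between scans (43%; 40% to 46% over the ±7-day window) can precede MGE if dosing starts at registration, and more if it starts later. The two biases oppose each other. Their net direction is unknown, and in a sample this small they cannot be assumed to cancel. DLT, the MTD and OS are not affected. This is a cheap improvement worth making, not a threat to the trial's main purpose.

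**What to change.** In section 6.1, footnotes a and b, and in section 7.2, state that a patient is evaluable for CR, PR or SD only if the baseline scan was taken after the last dose or fraction of prior anticancer treatment. Otherwise classify the patient as not evaluable for response, show the number so classified in both response tables, and keep the patient in the DLT, OS and PFS sets. Wording the rule for any prior anticancer treatment also covers treatments for which section 3.2.1 gives no interval.

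Beside each reported response, list the scan-to-first-dose interval and the date of last prior treatment. Section 4.0 already requires eligibility source documents at registration, and these should supply the dates. If the forms do not already capture them, two date fields are needed.

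This removes treatment overlap from the response tables. It does not correct growth before MGE, because the 42-day limit stays; it only makes that growth visible. The PFS reference scan is also unchanged, so PFS should be reported with that caveat. No extra scan is needed, and no dose or eligibility rule changes. The cost is a few lines of text and a slightly smaller response denominator.
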